### 5.2.2 Safety Objective(s)

To collect safety information, including type and number of AEs, SAEs, and device issues.

## 5.3 Study Endpoints

### 5.3.1 Primary Endpoints

The end points respectively to the objective number:

4. Echocardiographic measurements performed manually with Ligence Heart and comparator software. The inter-software reliability between manual measurements performed with Ligence Heart and other CE marked state-of-the-art medical image viewers will be calculated (Part 1 of the investigation);
5. Echocardiographic measurements performed automatically by Ligence Heart software and echocardiographic measurements performed manually by physicians. The accuracy of automatic functions of Ligence Heart will be compared with the accuracy of physicians performing measurements manually (Part 2 of the investigation);
6. Time used to perform echocardiographic measurements manually and time used to perform the measurements automatically.

### 5.3.2 Safety Endpoints(s)

Type and number of AEs, SAEs, and device issues.

## 6 Study Design

### 6.1 Summary of Study Design

Single center retrospective, randomized, quantitative clinical investigation, that will enroll subjects from the adult (aged >18 years) population that have undergone 2D TTE examination and have their study results saved in the investigation site's database during the period from 2010-08-01 to 2020-08-01. The study will be conducted in two stages, beginning with the Part 1, in which data will be generated for the assessment of the manual functionalities of Ligence Heart, followed by Part 2, in which data will be generated for the assessment of the automatic functionalities of Ligence Heart.

After both Part 1 and Part 2 of the study are finished, the analysis of the generated data will take place. The statistical conclusions formulated from the data will be used to fulfill the clinical investigation objectives and to either accept or reject the hypotheses of the clinical investigation.

The study will be conducted at the Republican Šiauliai Hospital (Respublikinė Šiaulių Ligoninė).

### 6.2 Study Population

Adult (aged >18 years) population that have undergone 2D TTE examination having various indications due to various cardiac pathologies and have their study results saved in the investigation site's database during the time period from 2010-08-01 to 2020-08-01.

UAB Ligence	Clinical Investigation Report	2021-04-09
		Rev: 1.0

The ultrasound machines that were used to perform the 2D TTE examinations that are included in the clinical investigation:

- GE Vivid E9 Ultrasound Machine;
- GE Vivid S5 Ultrasound Machine;
- Philips Affiniti 70 Ultrasound system;
- Philips EPIQ 7 Ultrasound system;
- Philips Sparq ultrasound system.

### 6.3 Number of Subjects

Required sample size was established with the help of statistical power calculation tool „G\*Power 3.1.9.7“, which estimates the minimum sample size required to find and statistically prove if there is an effect to be found. In the analyses that were carried out the sample size was calculated for Repeated measures, within-between interaction ANOVA. Obtained minimal sample size was established to be 54 for both Part 1 and Part 2 of the clinical investigation (Variables used in calculations are provided in the table below).

Coefficient	Value
Effect Size	0.25
$\alpha$	0.05
Power (1 - $\beta$ )	0.95
Number of groups	3
Number of measurements	2
Correlation among repeated measures	0.6

### 6.4 Protection of Vulnerable Subjects

The Sponsor shall avoid improper influence on, or inducement of, the subject, any investigator(s), or other parties participating in, or contributing to, the clinical investigation.

All investigators shall avoid improper influence on, or inducement of, the subject, Sponsor, other investigator(s), or other parties participating in, or contributing to, the clinical investigation.

### 6.5 Eligibility Criteria

#### 6.5.1 Inclusion Criteria

All included subjects will meet the following criteria:

- Aged 18 years at the time when the 2D TTE examination was performed;
- 2D TTE images are saved in the database of investigational site;
- Examination was performed during the time period of 2010-08-01 to 2020-08-01;
- 2D TTE images contain the following view modes that are necessary to perform the analysis of the images according to this clinical investigation plan:
  - apical 4 chamber view;
  - apical 2 chamber view;
  - parasternal long axis view.

#### 6.5.2 Exclusion Criteria

UAB Ligence	Clinical Investigation Report	2021-04-09
		Rev: 1.0

Subjects will be excluded that:

- Have anatomical or functional cardiac characteristics that prevent appropriate completion of 2D TTE image analysis using the study device - a list of such characteristics can be found in the section 4.6.2 Contraindications;

## 6.6 Recruiting and Screening

Studies will be randomly selected from time period 2010.08.01 – 2020.08.01 from the 2D TTE image database in Republican Šiauliai Hospital. The steps for including studies into the clinical investigation:

1. During the time period 2010.08.01 – 2020.08.01 Republican Šiauliai Hospital have stored 17410 2D TTE studies into their internal database, from which random studies are extracted as potential studies to be included in the clinical investigation.
2. Using a random number generator different numbers are generated (between 1 and 17410), each of which corresponds to one random number from the complete list of potential studies to be included.
3. IT specialist of the Investigational site extracts the chosen studies and provides the studies to the Principal Investigator.
4. Principal investigator assesses the chosen studies based on the inclusion/exclusion criteria. If the chosen study is found to be unsuitable based on the criteria, the Principal investigator requests a new randomly chosen study to be extracted by the IT specialist.
5. Once all required studies have been included in the clinical investigation, the Principal investigator extracts all required data from the subjects' files.
6. IT specialist assigns each of the studies a specific ID number which is then associated with the original study ID in the Investigational Site's database. Then all personal details from the studies are removed (including metadata, labels on the images themselves, etc.). This step completes the inclusion of subjects into the clinical investigation and the pseudonymized studies without any personal details are ready to be used for the Step 1 and Step 2 of the clinical investigation.

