### 4.7.2 Automatic functionalities

The device performs a series of steps that involve automated recognition of the echocardiography imaging data, recognition of echocardiographic probe position and detecting a set of anatomical (e.g. heart chamber borders, landmarks). The automated functionalities rely on the metadata obtained from the DICOM format (e.g. imaging mode) as well as predictions made by deep neural networks from the echocardiographic images (e.g. echocardiographic probe position recognition, heart chamber border, landmark detection).

To summarize, the input to the device is an echocardiography DICOM image. After the image is analyzed using automated and/or manual functionalities, a finalized report is generated, which is the output of the software.

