## 7.2 Subject Procedure

### Part 1

The purpose of the procedure in the Part 1 is to calculate the accuracy of Ligence Heart manual functions that are used to perform echocardiographic measurements comparing it with the accuracy of manual measurements performed with other CE marked state-of-the-art medical image viewers. Measurements made in Ligence Heart software will be compared with CE marked software “IntelliSpace Cardiovascular 5.1” (Phillips) and “EchoPAC” version 112 from GE Healthcare.

One cardiologist will perform 2D TTE measurements of each patient on each system 2 times. Time difference between repeated measures must be at least two days.

### Part 2

The purpose of the procedure in the Part 2 is to compare Ligence Heart automatic measurements accuracy and reliability with human cardiologists in real clinical setting.

Four physicians will make 2D TTE measurements of each subject study 2 times. Physicians cannot share thoughts or results between themselves. Time difference between repeated measures must be at least two days. Measurements of three physicians will be used in modeling and results of the 4th will be used as a validation with automated system.

During both parts, time used for the analysis of the 2D TTE images will be recorded. During manual 2D TTE image analysis, time it takes for physician to make measurements will be registered. Stopwatch starts when physician opens study in Ligence Heart and stops when all listed measurements are made. In the use case including automatic measurements, the time it takes for automatic system to make measurements and physician to correct/validate the results is registered.

Summary of the clinical investigation parts

#	Analysis	Purpose	TTE Examination Protocol	Measurements
Part 1	Manual Measurement Analysis	To calculate the accuracy of Ligence Heart manual functions that are used to perform echocardiographic measurements comparing it with the accuracy of manual measurements performed with other CE marked state-of-the-art medical image viewers.	One physician will make 2D TTE measurements of each patient on each system 2 times. Time difference between repeated measures must be at least two days.	
 
• AoS (PLA)
 
• RVB (A4CH)
 
• LVEDV (A4CH)
 
• LVEDV (A2CH)
 
• RVEDA (A4CH)
 
• RAA (A4CH)
 
• AV-Vmax
 

UAB Ligence	Clinical Investigation Report	2021-04-09
		Rev: 1.0

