## 14.2 Storage of Images and Associated Health Data

Research images and associated data will be collected and disclosed to the Sponsor as part of this study. Fully de-identified data, which has had all personal identifying information removed, may be stored and used by the Sponsor indefinitely. The Sponsor and/or its authorized representatives may use any de-identified data collected in this study for future technology and engineering development, marketing purposes, education, regulatory claims, or other possible uses.

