### 16.4 Special considerations and limitations

All patients in our testing cohort had sinus rhythm which means that caution should be used in cases of cardiac arrhythmia. Additionally, all of our validation data comes from a single center in Lithuania and echocardiographic images are obtained from two manufacturers (GE and Philips) ultrasound machines. Our aims for the post-market clinical follow-up are directly related to the aforementioned limitations. We aim to expand our validation study in multiple centers, in order to include participants with cardiac arrhythmias and include studies from a higher variety of ultrasound machines.

UAB Ligence	Clinical Investigation Report	2021-04-09
		Rev: 1.0

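### The Part 2 test studies are drawn from the site's complete archive with no rule excluding patients whose images were used to develop the deep-learning algorithms

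*Protocol*

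**What the plan says.** **Sampling frame.** Protocol section 6.6 says that "Republican Šiauliai Hospital have stored 17410 2D TTE studies into their internal database" over the ten-year window, "from which random studies are extracted as potential studies to be included in the clinical investigation". Random numbers from 1 to 17,410 are then generated, "each of which corresponds to one random number from the complete list of potential studies to be included". The investigator screens each drawn study against the eligibility criteria and requests another random study if one is unsuitable (step 4). Each study receives an ID that is linked to its original ID in the site database (step 6).

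**Eligibility.** Section 6.5.1 asks for age, storage in the site database, examination date and three views. Section 6.5.2 has one exclusion, for subjects who "Have anatomical or functional cardiac characteristics that prevent appropriate completion of 2D TTE image analysis using the study device", and refers to the list in section 4.6.2.

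**Bias control.** Section 3.2 names two measures: random selection and removal of identifying information.

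**Device.** Section 4.7.2 says the automatic functions rely on image metadata and on "predictions made by deep neural networks from the echocardiographic images". Section 16.2 adds that quality thresholds act at each step and suppress low-confidence values. Section 4.9 refers algorithm detail to a Technical File.

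**Claim.** Section 15.2 uses the fourth cardiologist as the benchmark, and section 16.2 concludes that automatic accuracy is non-inferior to a cardiologist. Section 16.4 calls the 58 subjects a testing cohort. It does not say that they are independent of the development data.

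**The concern.** A trained network tends to do better on images, or on patients, that it has already met during development. The Part 2 accuracy claim therefore needs test studies that played no part in training, tuning or threshold setting. Under sections 6.5 and 6.6 as written, a development study held in this archive would be eligible, and site staff would have no criterion for rejecting it.

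Random selection does not remove the problem. It prevents hand-picking, but if part of the archive was used in development, a random draw carries that share into the test set on average. The frame also counts studies rather than patients, so a different examination of a development patient could be drawn.

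Any bias would run one way. Prior exposure could help Ligence Heart, while the fourth cardiologist gains nothing from it. Part 1, which tests manual tools, is not affected.

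The sampling frame and the eligibility rules are fixed in this document, so the point is not one that is normally left to a statistical analysis plan.

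**Working it through.** **1. The plan's own figure.** Section 12.2 gives a minimum of 54 for the within-between interaction in a repeated-measures ANOVA, with f = 0.25, alpha = 0.05, 3 groups, 2 measurements and correlation 0.6. With noncentrality f² × N × m / (1 − ρ), and (k − 1)(m − 1) and (N − k)(m − 1) degrees of freedom:
- N = 54: noncentrality 0.0625 × 54 × 2 / 0.4 = 16.9, power 0.956.
- N = 51: power 0.943.

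The smallest N divisible by 3 that reaches 0.95 is 54, so the figure reproduces. It does not depend on how the frame is defined.

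**2. Is there a rule that removes development studies?**

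| Place | What it filters on | Development use? |
|---|---|---|
| 6.5.1 | age, storage, date, views | no |
| 6.5.2 with 4.6.2 | cardiac conditions, procedures, implanted devices | no |
| 6.6 | random number, then 6.5 | no |
| 3.2 | random selection, de-identification | no |

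No section says where the development images came from.

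**3. Chance of overlap.** Inputs: 58 studies analysed (section 15.1) and a frame of 17,410 (section 6.6). Let q be the share of the archive that belongs to patients used in development. The document does not give q, so it is assumed. Ignoring the eligibility screen:

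P(at least one of 58 overlaps) = 1 − (1 − q)^58; expected overlap = 58q.

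| q (assumed) | Expected overlap | P(at least one) |
|---|---|---|
| 0 | 0 | 0% |
| 0.5% | 0.3 | 25% |
| 1% | 0.6 | 44% |
| 2% | 1.2 | 69% |
| 5% | 2.9 | 95% |

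Drawing without replacement (hypergeometric) gives the same rounded values; for instance, 174 development studies among 17,410 give 44%.

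**4. Room in Table 3.** Eleven of the 21 rows have fewer than 58 studies because the confidence filter withheld values: four rows stand at 54, four at 55 and three at 56. In a row at 54, losing one study leaves 53.

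**The case against.** The strongest reply is that no leakage is shown. Nothing in the document says that an image from this hospital was used in development, and the Technical File, which is not at hand, may show that none was. In that case q = 0 and one sentence would settle the matter for these 58. This stands, and it is why the point is an unguarded risk. It does not close the gap, because this document both fixes the frame and makes the accuracy claim without stating independence.

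A second reply is that the proposed check may not be possible. It needs development records that can be linked to site IDs, while in this study the sponsor receives only pseudonymized data. That also stands as a limit on the fix.

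Four stronger readings are tempting and are not supported:
- **One overlapping study would overturn a verdict.** Left atrial diameter passes Table 3 at 55/58 against 58/58. A two-sample t-test gives p = 0.0805, and 54/58 would give p = 0.042. But dropping a study cannot add a disagreement. With the agreement limits held fixed, p stays at 0.0805 with 57 studies left and 0.0799 with 48. A reversal would need an overlapping study that agreed only because it had been seen before, and nothing in the document allows that chance to be estimated.
- **Section 7.2 trains on the test set.** It says "Measurements of three physicians will be used in modeling and results of the 4th will be used as a validation with automated system", but sections 12.5.2 and 15.2 show that the three physicians' readings feed the ANOVA and set the variability baseline.
- **Section 14.2 contaminates the result.** The permission for engineering use concerns the future and cannot bias results already obtained.
- **The expansion in section 16.4 reuses these studies.** The text speaks of more centres, arrhythmia patients and more machines. It does not say that the 58 will be scored again.

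**Conclusion.** The concern holds as a gap in the sampling rule. The frame is the whole archive, and no eligibility, screening or bias-control provision keeps development patients out of Part 2. If there was overlap, Ligence Heart's agreement rates would tend to be too favourable against the fourth cardiologist.

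The size cannot be fixed from the document. The chance of any overlap runs from nil at q = 0 to 95% at q = 5%, where about 3 of the 58 studies would be affected. These figures assume a value for q and ignore the eligibility screen. They give the chance of overlap, not the amount of bias, which the document gives no means of estimating.

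A reader might infer that the Part 2 result is contaminated or that a Table 3 verdict would change. Neither is shown. The point should be fixed because the remedy is specific and cheap and because the accuracy claim depends on unseen images.

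**What to change.** **Plan.** Add to section 6.5.2 a patient-level exclusion of anyone whose images were used to train, tune or set the quality thresholds of Ligence Heart version 2.1. In section 6.6, apply it to the list of 17,410 before random numbers are drawn.

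**Completed cohort.** Check the 58 against the development records through the ID link of section 6.6 step 6. If no data from this site were used in development, a written statement to that effect can take the place of the check. Report the overlap even if it is zero. If there is any, either replace those studies by further random draws under step 4, or re-issue Table 3 without them, giving the revised N for each row.

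**Cost.** One exclusion sentence and one record match; if overlap is found, also a re-run of Table 3, plus new readings where studies are replaced. The frame shrinks slightly and the required 54 is unchanged. If studies are dropped without replacement, the rows now at 54 may fall below that number. The match is feasible only if the development records can be linked to site IDs; if they cannot, the report should say so.

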## 6.7 Criteria for Withdrawal/Discontinuation

A subject may withdraw from study participation at any time, for any reason. The study staff may withdraw a subject at any time, for any reason. The reasons for withdrawal and discontinuation for any subject shall be recorded to the Sponsor-provided case report form (CRF). These will be reported to the Sponsor.

# 7 Study Procedures

## 7.1 Study Parts

No direct clinical procedures will be performed on the enrolled subjects. The procedure that will take place is the analysis of the 2D TTE examination DICOM images that were included in this study. Once enough subjects are chosen and enrolled in the study, the following parts take place:

During Part 1 of the study, investigators will analyze the same images using Ligence Heart software, Intellispace Cardiovascular 5.1 software, and EchoPAC version 112 software. The purpose of part 1 is to calculate the accuracy of the manually made measurements on the Ligence Heart software with other CE marked state-of-the-art software.

During part 2 of the study, investigators will analyze 2D TTE images and the results will be compared to the results of the analysis that automatic functionalities of Ligence Heart allow. The purpose of part 2 is to compare Ligence Heart automatic measurements precision and reliability with human physicians in real clinical setting.

Study Parts

UAB Ligence	Clinical Investigation Report	2021-04-09
		Rev: 1.0

Study Part	Functionalities tested	Comparator
Part 1	Manual	Other state-of-the-art CE marked medical images analysis software: Intellispace Cardiovascular 5.1 by PHILIPS, and EchoPAC version 112 software by GE
Part 2	Automatic	Cardiologists with expertise in echocardiology

## 7.2 Subject Procedure

### Part 1

The purpose of the procedure in the Part 1 is to calculate the accuracy of Ligence Heart manual functions that are used to perform echocardiographic measurements comparing it with the accuracy of manual measurements performed with other CE marked state-of-the-art medical image viewers. Measurements made in Ligence Heart software will be compared with CE marked software “IntelliSpace Cardiovascular 5.1” (Phillips) and “EchoPAC” version 112 from GE Healthcare.

One cardiologist will perform 2D TTE measurements of each patient on each system 2 times. Time difference between repeated measures must be at least two days.

### Part 2

The purpose of the procedure in the Part 2 is to compare Ligence Heart automatic measurements accuracy and reliability with human cardiologists in real clinical setting.

Four physicians will make 2D TTE measurements of each subject study 2 times. Physicians cannot share thoughts or results between themselves. Time difference between repeated measures must be at least two days. Measurements of three physicians will be used in modeling and results of the 4th will be used as a validation with automated system.

During both parts, time used for the analysis of the 2D TTE images will be recorded. During manual 2D TTE image analysis, time it takes for physician to make measurements will be registered. Stopwatch starts when physician opens study in Ligence Heart and stops when all listed measurements are made. In the use case including automatic measurements, the time it takes for automatic system to make measurements and physician to correct/validate the results is registered.

Summary of the clinical investigation parts

#	Analysis	Purpose	TTE Examination Protocol	Measurements
Part 1	Manual Measurement Analysis	To calculate the accuracy of Ligence Heart manual functions that are used to perform echocardiographic measurements comparing it with the accuracy of manual measurements performed with other CE marked state-of-the-art medical image viewers.	One physician will make 2D TTE measurements of each patient on each system 2 times. Time difference between repeated measures must be at least two days.	
 
• AoS (PLA)
 
• RVB (A4CH)
 
• LVEDV (A4CH)
 
• LVEDV (A2CH)
 
• RVEDA (A4CH)
 
• RAA (A4CH)
 
• AV-Vmax
 

UAB Ligence	Clinical Investigation Report	2021-04-09
		Rev: 1.0

		Measurements made in Ligence Heart software will be compared with CE marked software "Tomtec" ("IntelliSpace Cardiovascular 5.1") (Phillips) and „EchoPAC“ version 112 from GE Healthcare.		
 
• TR-Vmax
 
• E
 
• S'RV
 
• DEC
 
• ACT
 
• AV-VTI
 
• TR-VTI
 
• LVEDV (A2CH + A4CH)
 

Part 2	Automatic Measurement Analysis	To compare Ligence Heart automatic measurements precision and reliability with human physicians in real clinical setting.	Four physicians will make 2D TTE measurements of each patient 2 times. Physicians cannot share thoughts or results between themselves. Time difference between repeated measures must be at least two days. Measurements of three physicians will be used in modeling and results of the 4th will be used as a validation with automated system.	
 
• RAMAD (A4CH)
 
• AoA
 
• AoS
 
• STJ
 
• AAo
 
• LAD (PLA)
 
• LAV
 
• IVSd
 
• LVPWd
 
• LVEDD
 
• LVESD
 
• LVEDV (A4CH)
 
• LVESV (A4CH)
 
• LVEDV (A2CH)
 
• LVESV (A2CH)
 
• RAA
 
• RVB
 
• RVM
 
• RVOTPD
 
• RVEDA
 
• RVESA
 

	Time used Comparison	To compare Ligence Heart automatic measurement tool execution time with time it takes a physician to perform measurements manually.	During manual TTE analysis, time it takes for physician to make measurements will be registered. Stopwatch starts when physician opens study in Ligence Heart and stops when all listed measurements are	Time to perform measurements with automatic functions vs. time to perform measurements without automatic functions.

UAB Ligence	Clinical Investigation Report	2021-04-09
		Rev: 1.0

			made. In the use case including automatic measurements, the time it takes for automatic system to make measurements and physician to correct/validate the results is registered.	
--	--	--	--	--

